The Social Isolation Short Form 4a, derived from the more extensive UCLA Loneliness Scale, is a globally recognized tool for measuring loneliness. It aligns with the UK's Office for National Statistics recommendations for assessing loneliness (ONS, 2018) and has demonstrated reliability in gauging social isolation. Although a more detailed version, the Social Isolation Short Form 8a, is available and offers increased reliability, its length might be burdensome for weekly assessments. Therefore, this study proposes using the shorter form as a primary outcome. It will be administered weekly, following each individual therapy session.

Service use

To determine if there is any potential cost saving for the NHS, we will ask participants to consent to the research team to take a record of:

- Unplanned contact with the service
- A and E attendances
- Crisis line contacts
- Days in psychiatric hospital
- Days spent in general hospital

Self harm and suicidal behaviour

To determine if there has been any reduction in self-harm and suicidal behaviour, we will ask participants to consent to the research team to take a record of:

- Incidents of self-harm recorded in the clinical record
- Incidents where the participant has engaged in self-injury or self-neglect where their intent was to cause life threatening injury.

3.2 Secondary Outcome:

Other Routine Outcome Measures: Quality of Life, Patient Satisfaction, and Suicidality

In addition to the weekly assessments, participants will complete three other questionnaires at start of baseline, start of treatment, 6 months, 12 months, 18 months into the treatment and at the end of follow-up. These scales evaluate quality of life (ReQol), patient satisfaction (Dialogue), and suicidality (Columbia Scale).

*ReQoI: The Recovering Quality of Life (ReQoI-10) scale tracks perceived changes in 'quality of life' over time. This 10-item scale is validated for individuals aged 16 and above. Scores range between 1 and 5, and a shift of 5 points on the scale indicates 'significant improvements' (Keetharuth et al., 2018).

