3.4 Primary endpoint/outcome

Reductions in the LPFS 2.0 and Social Isolation short form 4.0 constitute a potential benefit. We have chosen these outcome measurements as they are used internationally, recommended by ICHOM, and have been validated for use in older adults. We are measuring personality functioning and social isolation as our primary measures. We are making comparisons between baseline functioning, and across participants to power the study. Measurements are taken weekly from start of the waiting period, for the duration of the treatment phase, and at follow up.

The primary endpoint will be whether personality function (as measured by the LPFS 2.0) and social isolation (as measured by the social isolation short form 4.0) have changed during 24 months. Significant decreases in both measures will indicate that MBT is effective at improving personality functioning and decreasing social isolation.

Additionally, if participants had any incidents of suicidal behaviour or self-harm, then a reduction in frequency of these events will constitute a potential benefit. As older people may keep suicidal behaviour and self-harm hidden, there is an expectation that participants may not make disclosures around these issues at baseline.

Taking data pertaining to service use may provide a limited indication as to whether any potential cost savings are associated with the intervention. Due to the limited number of participants, there is a recognition that statistical test on these findings may not reach statistical significance.

Any reduction in self-harm, suicidality, or service use may also represent efficacy.

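### Section 3.4 lets any fall in about eight service-use, self-harm and suicidality outcomes be read as efficacy, with no size, time point or link to the planned tests

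*Protocol*

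**What the plan says.** Under its primary endpoint heading, protocol section 3.4 treats two groups of outcomes differently.

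- **Weekly scales (LPFS 2.0 and Social Isolation Short Form).** MBT is to be called effective if both fall significantly.
- **Service use, self-harm and suicidality.** A lower frequency of self-harm or suicidal behaviour is called a potential benefit, and service use a limited indication of cost saving. Because numbers are small, "there is a recognition that statistical test on these findings may not reach statistical significance". The section then ends: "Any reduction in self-harm, suicidality, or service use may also represent efficacy".

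The outcomes are listed in sections 3.1 and 3.2. Section 3.1 collects service-use data to look for possible NHS savings and lists five items, namely "Unplanned contact with the service", "A and E attendances", "Crisis line contacts", "Days in psychiatric hospital" and "Days spent in general hospital". It adds two counts, one of recorded self-harm and one of acts with life-threatening intent. Section 3.2 names the Columbia Scale as the measure of suicidality.

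The table in section 3.7 has the clinical-record data taken at 0, 6, 12, 18 and 24 months. Section 10.3.2 plans a Friedman test across phases for service use and self-harm. Section 10.3.3 plans a Friedman test and a Reliable Change Index for the Columbia Scale. Section 10.3.1 states that there is no between-group comparison.

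**The concern.** The closing sentence of section 3.4 says what may count as efficacy, and nothing in it would stop the claim. It gives no minimum change, interval, test or time point. It does not mention section 10.3, and several outcomes can each supply the reduction. In a small uncontrolled before-after study, event counts go up and down by chance, so a fall somewhere is the usual result even when the treatment does nothing.

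Cost saving and risk reduction are part of the study hypothesis. Section 2 says the study will inform a future RCT, and section 10.10 marks economic evaluation as not applicable, so these raw records are the main basis for any cost statement. A reading of efficacy that is open under most null results would carry little information into that next step.

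**Working it through.** **1. The plan's own figure.** The only computed figure is in section 10.1: power close to 1 with n = 10 and Cohen's d = 1. It was checked by simulating 10 participants with 8 baseline and 72 treatment scores (Appendix 4) and autocorrelated errors. A phase permutation test on thinned data was used, with individual p-values combined by their sum and an assumed one-sided alpha of 0.05. Power was 1.00, 1.00, 1.00 and 0.98 at autocorrelations of 0, 0.3, 0.5 and 0.7, so the figure is reproduced. It concerns the weekly scales. The protocol gives no error rate for the sentence at issue.

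**2. Number of outcomes.** Five service-use items + two self-harm or suicidal-behaviour counts + the Columbia Scale = 8.

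**3. No effect, independent outcomes.** If each outcome falls with probability p, the chance of at least one fall among k outcomes is 1 − (1 − p)^k.

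- k = 8, p = 0.5: 1 − 0.5^8 = 0.996
- k = 7 (record-based outcomes only), p = 0.5: 1 − 0.5^7 = 0.992
- k = 3 (the three domains the sentence names), p = 0.5: 1 − 0.5^3 = 0.875
- k = 8, p = 0.25 (rare events, many ties): 1 − 0.75^8 = 0.900

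**4. No effect, correlated outcomes.** The changes are taken as normal with common correlation r and mean zero. At r = 0.5 the chance that none of k falls is 1/(k + 1), so for k = 8 the result is 1 − 1/9 = 0.889. Other values were computed numerically.

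| r | 8 outcomes | 3 outcomes |
|---|---|---|
| 0 | 0.996 | 0.875 |
| 0.3 | 0.948 | 0.802 |
| 0.5 | 0.889 | 0.750 |
| 0.7 | 0.807 | 0.690 |

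For eight outcomes the chance drops below 90% once r exceeds about 0.47.

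**5. No effect, event counts.** Poisson counts were simulated for 10 participants in two equal six-month windows with unchanged rates and gamma-distributed differences between people. Assumed mean events per person per window ran from 0.05-0.5 (low scenario) to 0.2-3 (high scenario).

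| Dependence assumed | Chance that at least one total falls |
|---|---|
| Eight outcomes, each with its own person effect, window effect per person (variance 0 to 1) | 0.91-0.99 |
| Eight outcomes, person effect shared across outcomes | 0.81-0.99 |
| Eight outcomes, period effect common to all participants and outcomes | about 0.66-0.82 |
| Three outcomes (means 0.5, 0.3, 0.2; window variance 0.5) | 0.77 |

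In the first row, even at the largest window variance, the mean correlation between changes is only about 0.13 to 0.32. That row therefore represents weak to moderate dependence.

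A separate simulation of the seven record-based outcomes, with 10 or 14 participants, gave 0.86-0.99 for one before-after comparison with no shared effect. It gave 0.68-0.88 when outcomes rise and fall together within a participant. If a fall at any of the four later time points counts, the range is 0.85-1.00.

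**6. What a test would change.** If each of eight independent outcomes had to fall significantly at an assumed 0.05 level, with no adjustment, the chance of at least one false signal would be 1 − 0.95^8 = 0.337, against 0.996 for a bare decrease.

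**The case against.** The strongest case on the other side has five parts.

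- **The sentence is hedged.** It says such a reduction may represent efficacy. The firm statement in section 3.4 concerns the weekly scales only. This stands: a reader might infer a formal success rule here, and the text does not support that.
- **Tests are planned.** Sections 10.3.2 and 10.3.3 provide Friedman tests, and the Reliable Change Index sets a minimum size for individual change on the Columbia Scale. A reader might infer that the closing sentence is the only basis for conclusions, or that section 3.4 waives significance testing. Neither holds. The remark about significance is a caveat about power and presupposes testing. What remains is that the closing sentence is not tied to those analyses.
- **A time point exists elsewhere.** Section 3.3 puts the study endpoint at 24 months. The closing sentence does not refer to it, and section 3.7 lists four post-baseline extractions. The single-comparison figures above do not depend on this.
- **The chance of a false signal may be lower.** A&E visits, crisis contacts, admissions and self-harm plausibly move together. Hospital days cluster. Section 3.4 expects under-disclosure at baseline, which makes a recorded fall in self-harm less likely. All of this is fair, and it is why the range extends down to about two-thirds. Under-disclosure does not, however, make falls in A&E visits or bed days less likely.
- **It is a pilot of 10-14 people.** Confirmatory error control across eight exploratory outcomes would be a matter of preference. This also stands, and it favours descriptive reporting over reading efficacy from any fall.

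**Conclusion.** The point holds as a defect in a stated interpretive sentence. Under no effect, at least one of about eight outcomes falls by chance in roughly two-thirds to nearly all trials, so the sentence as written has little ability to tell an effective programme from an ineffective one.

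A reader might infer that the false-signal rate exceeds 90% in general. The documents do not fix that. It requires weak to moderate correlation and enough events to give each outcome a reasonable chance of falling, or several chances over time. The protocol states no event rates, correlations or significance level, so every figure here rests on assumptions. The conclusion does not depend on where in the range the truth lies. The planned analysis of the two weekly scales is unaffected.

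**What to change.** Delete the last sentence of section 3.4 and replace it with:

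> Changes in service use, self-harm and suicidality will be reported descriptively for every listed outcome, increases and decreases alike, per unit of observation time (mean change for the Columbia Scale) with 95% confidence intervals, alongside the tests in section 10.3. A decrease alone will not be interpreted as evidence of efficacy or cost saving; where the interval includes no change, the result will be reported as inconclusive.

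No Holm or similar adjustment is needed for this exploratory reporting.

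The cost is one wording change and some intervals from data already being collected. The downside is that a statement of benefit on these outcomes will seldom be possible with 10-14 participants, which section 3.4 already anticipates for service use.

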3.5 Secondary endpoints/outcomes

Other endpoints include measures of 'quality of life', satisfaction, and suicidality. These measures will be taken at 6 monthly intervals.

3.6 Exploratory endpoints/outcomes

Qualitative interviews will be conducted to determine acceptability. See section on qualitative methods.

3.7 Table of endpoints/outcomes

Objectives	Outcome Measures	Timepoint(s) of evaluation of this outcome measure (if applicable)
Primary Objective Personality Functioning Social isolation	LPFS 2.0. Social Isolation Short Form 4.0	Both questionnaires are given from day 0 till the end of data collection period at 24 months. Patients are requested to fill out these two questionnaires on a weekly basis during waiting period, treatment and follow up.
Service use Self injury and suicidal behaviour	Service use Suicidal behaviour	Data to be taken from clinical records at 0,6,12,18, and 24 months
Feasibility	Comparison of recruitment rate, drop out, and completion	Data to be taken at 0, 6, 12, 18, 24 months
Acceptability	Thematic analysis of qualitative interview	Analysis of data at 24 months
Secondary Objectives		
To evaluate	ReQoL 10	Measures provided at 6 month
quality of life (ReQol),		intervals, at 0,6,12,18, and 24 months.
patient satisfaction (Dialogue),	Dialogue	months.
and suicidality (Columbia Scale).	CSRSS (Columbia Scale)	

4 TRIAL DESIGN

Design:

This study uses a multiple single case series design, a form of Single Case Design (SCD). It will employ quantitative methods to track changes in personality functioning over time using the LPFS 2.0 scale and changes in loneliness using the Social Isolation Short Form 4a. Data from a participant will be compared within the participant between treatment phases (baseline, treatment and follow up), so participants serve as their own controls. Initial data collection will take place at an outpatient clinic in Manchester, United Kingdom. Data will be gathered weekly away from the MBT clinic. The research team, primarily involved in clinical practice, will utilize an established older adult MBT service in Manchester for the sample. This approach mitigates some challenges of assessing multi-modal

psychological treatments, as there's no need for the research team to establish a new therapy program.

A multiple single case series design will enhance experimental control since participants serve as their own control. In order to get a stable and representative estimate of the baseline state all participants will have a waiting period of 8 weeks before starting treatment. Participants who drop out of the research completely during this phase won't have any further data collected We will ask anyone who drops out of the therapy to consent to providing data relating to their reason for drop out.

The strength of a SCD study is that it produces statistical power by taking a large number of data points with a small number of participants. Due to the high number of data points per participant, change to outcome measurements can accurately be described. Additionally, due to the low number of participants, there is a lower cost to the intervention, which means that it is more feasible to carry out long term studies of psychological treatments for personality disorder, which often span multiple years.

5 TRIAL SETTING

The trial will take place in one centre in an extant MBT for older adults service. The service is already operational, and as such local policies and procedures will be adhered to except where explicitly mentioned.

The treatment team will comprise of psychotherapists who have completed their basic and follow-up MBT training.

The patient population will be older people (over 65) in Manchester, who meet the criteria for personality disorder, or who are sub threshold to a diagnosis (score one point lower than the cutoff point in DSM-5). Participants will be recruited from later life CMHTs in Greater Manchester.

6 PARTICIPANT ELIGIBILITY CRITERIA

6.1 Inclusion criteria

- Resident of Manchester, England.
- Aged 65 or over.
- Confirmed Personality Disorder diagnosis via the Structured Clinical Interview for DSM 5 Personality Disorders (SCID-5-PD) or significant associated traits (Personality Disorder trait specified according to DSM-5). If individuals don't fully meet the criteria, their sub-threshold presentation will be explicitly noted (one criterium less than the cut off point for the personality disorder).
- Ability to provide informed consent.
- Under the care of a local community mental health team.

6.2 Exclusion criteria

- Primary issues related to psychosis, dementia, or mild cognitive impairment.
- Primary concerns associated with anti-social personality disorder or significant violent/aggressive traits.
 - Ability to attend the outpatient clinic (free transport provided).

A diagnosis of autism won't be an exclusion criterion if all other inclusion criteria are met. The study's service site has seen referrals for individuals with autism over the past 18 months, and they've shown improvement in their outcome measures.

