7.1 Recruitment

Participants will come from a Later Life MBT service in Manchester, which exclusively serves older adults and offers a comprehensive MBT program. The study aims to collect data from 10 older adults for an 18-month treatment duration. As the population is likely to have multiple physical comorbidities, the study will aim to recruit 14 participants, with the expectation that there will be some attrition in the screening and introductory phases.

Single Case Experimental Design studies consider several factors for power, including participant count, observations, inter-participant correlation, and the likelihood of false positives (Shadish et al., 2014). To ensure adequate power, we'll collect weekly outcome data on personality functioning using the LPFS 2.0 and data on loneliness using the Social Isolation Short Form 4a before, during and after the 18 months treatment from the participants.

Participants will be sourced from an existing later life MBT service. All will have a confirmed personality disorder diagnosis based on the DSM-5 structured clinical interview (SCID-5-PD) or subthreshold. Those not meeting this criteria will not be excluded from the service if MBT is clinically indicated. When participants fulfil only one criterium under the cutoff point at the SCID5-PD interview, they will also be included in the study, but it will be clearly indicated that they are 'sub-threshold' to a full diagnosis of personality disorder.

Typically, referrals to the later life MBT service come from older adult community-based mental health teams in England, overseen by the NHS. All study participants will receive standard treatment, including regular meetings with a mental health professional and periodic reviews with a consultant psychiatrist. No restrictions will be placed on participants seeking other treatments, though concurrent psychological treatments might be contraindicated.

All participants will be aged 65 or older, with no upper age limit. The study won't control for other demographics, except that participants must reside in Manchester. Free transport can be arranged for participants, and in rare cases, treatment can be provided at home or in hospital wards due to frequent treatment disruptions from physical ailments or illnesses in older adults.

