10.8 Procedure(s) to account for missing or spurious data

The primary outcome data will be gathered weekly before each participant's individual MBT session, either by the therapist or via phone if the participant is absent. The secondary outcome measures will be collected by the research assistant. Patients will be attending at least weekly sessions at the location, so the research assistant and therapists will have regular contact with the participants to remind them to fill out the questionnaires.

In case of missing data we will try to find the reason that the participant did not fill out the questionnaire. In case of random missing data the data analysis contain an implicit imputation. In case of drop-out we will try to describe the reason for drop-out, because we are interested whether this treatment is feasible for older patients with personality disorders.

10.9 Other statistical considerations.

In case of slow recruitment rate an amendment to this protocol will be submitted to request for extension the recruitment period of 3 years.

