*ReQol: The Recovering Quality of Life (ReQol-10) scale tracks perceived changes in 'quality of life' over time. This 10-item scale is validated for individuals aged 16 and above. Scores range between 1 and 5, and a shift of 5 points on the scale indicates 'significant improvements' (Keetharuth et al., 2018).

Dialogue: The Dialogue Satisfaction Scale gauges 'patient satisfaction' concerning their quality of life and the treatment they receive. This 11-item scale can be analysed item-wise or by calculating a mean score across all items. In this study, an overall mean score will be used, which ranges from 1 to 7. Scores above 5 suggest high satisfaction, potentially indicating that secondary mental health care might no longer be necessary. Conversely, scores below 4 highlight explicit dissatisfaction, warranting "particular attention" (Mosler et al., 2020).

Columbia Scale: The Columbia Suicidality Response Severity Scale (CSRSS) offers a preliminary indication of an individual's suicide risk. It contains xx items and total or mean scores range from 0 to 1. While it should be used alongside other risk assessment tools, it serves as an initial screening tool for potential suicide risk in adults. The scale has shown sensitivity to changes in suicidality over time (Posner et al., 2011).

Initial screen and evaluation:

Structured Clinical Interview for DSM-5 Personality Disorders

This measure is a validated tool for assessing DSM-5 personality disorders. It has been used with both younger and older adults. There is a procedure for delivering the interview and scoring it. All three members of the team that will deliver this interview have been trained in its use.

Additional processes

To ensure adequate data collection, all outcome measurement forms will be provided to each participant weekly, at their face to face appointment. If the participant does not attend a session, then they will be asked to complete the questionnaire at the next available appointment. Data will be securely stored on a database that will not be accessible by the treatment team, and will only be accessible by the data management and collection team.

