13.5 Protocol compliance

Prospective, planned deviations or waivers to the protocol are not allowed under the UK regulations on Clinical Trials and must not be use. Accidental protocol deviations can happen at any time. They must be adequately documented on the relevant forms and reported to the Chief Investigator and Sponsor immediately. Deviations from the protocol which are found to frequently recur are not acceptable, will require immediate action and could potentially be classified as a serious breach.

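### Section 6.2 lists being able to attend the clinic as a reason for exclusion, the reverse of what the rest of the protocol assumes

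*Protocol*

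**What the plan says.** Section 6.2 of the protocol (Exclusion criteria) has three bullets. The first is "Primary issues related to psychosis, dementia, or mild cognitive impairment". The second concerns anti-social personality disorder and marked violent or aggressive traits. The third is "Ability to attend the outpatient clinic (free transport provided".

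Section 6.1 (Inclusion criteria) has five bullets: residence in Manchester, age, a personality disorder diagnosis or sub-threshold presentation, ability to consent, and "Under the care of a local community mental health team". None concerns attendance.

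Section 7.1 (Recruitment) says that free transport can be arranged and that "in rare cases, treatment can be provided at home or in hospital wards", and gives treatment disruption from physical illness as the reason. Section 13.5 (Protocol compliance) says: "Prospective, planned deviations or waivers to the protocol are not allowed".

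**The concern.** An exclusion criterion tells screening staff whom to turn away. This one tells them to turn away people who can attend, and those are the people an outpatient therapy programme is meant for. If staff follow it, the intended population is barred. If they quietly reverse it, they enrol against the approved text, and the protocol gives them no authority to do so.

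A smaller uncertainty remains even when the bullet is read the other way round. Section 7.1 provides for treatment at home or on a ward in rare cases. The protocol does not say whether a person who cannot attend at all may be enrolled on that basis.

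**Working it through.** No arithmetic applies. The check is a comparison of the sections that bear on attendance.

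1. **Direction of the bullet.** It stands complete under the exclusion heading, after two bullets that are ordinary reasons to exclude. As written, meeting it excludes.

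2. **Whether Section 6.1 offsets it.** It does not. None of the five inclusion bullets mentions attendance, so no second statement points the other way.

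3. **What the rest of the protocol assumes.**
   - Section 4: "Initial data collection will take place at an outpatient clinic in Manchester, United Kingdom".
   - Section 7.1.2: screening treats attendance and transport as practical matters to be dealt with before the programme starts.
   - Section 8.1: treatment consists of a weekly individual session and a weekly group session.
   - Section 10.8: "Patients will be attending at least weekly sessions at the location".
   - Section 11.1: "all outcome measurement forms will be provided to each participant weekly, at their face to face appointment".

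   Some text on data collection is looser. Section 4 also has the weekly measures completed away from the clinic, and Section 10.8 allows collection by phone when a participant is absent. These provisions concern how forms are completed. They do not suggest that participants stay away from therapy.

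4. **Who is left under the literal reading.** Only people unable to attend. Section 7.1 foresees treatment away from the clinic only in rare cases. The literal criterion therefore leaves a population for whom the protocol makes only exceptional provision.

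5. **Whether staff may simply read it as intended.** Section 13.5 rules out planned deviations and waivers. Knowingly enrolling a person who meets a listed exclusion is not an accidental deviation of the kind that section says to document and report. The route open to the sponsor is an amendment.

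6. **What reversing the bullet leaves open.** Either repair, as an inclusion criterion or as an exclusion for inability to attend, would bar a person who cannot attend. Section 7.1 does not say whether its home and ward provision applies only after enrolment, so the two sections need to be read together and made explicit.

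**The case against.** The strongest reply is that nobody who reads the whole protocol could think that attenders are excluded. The transport note in the same bullet gives the intent away, and the setting, screening and treatment sections all agree with it. Staff would very probably never apply the bullet literally. That is right, and it limits the practical consequence. It does not remove the error, because eligibility is checked and audited against the written criterion.

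Three stronger readings are tempting, and the documents do not support them.

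- **Serious breach.** A reader might infer from Section 13.5, which says that recurring deviations may be classed as a serious breach, that normal enrolment would become one. Section 13.6 sets the test: a likely significant effect on participants' safety or integrity, or on the scientific value of the trial. Enrolling people who can attend a clinic-based therapy is not shown to meet it. To say that all of the 10-14 planned enrolments would contravene the criteria only restates the sample size under the literal reading. It measures no harm or bias.

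- **Primary outcome.** A reader might infer that the denominator of the recruitment and consent rates is undefined. Section 3.1 names these rates but refers their targets to a separate table that is not in the document. No section makes the people eligible under Section 6.2 the denominator of either rate.

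- **Contradiction with Section 7.1.** A reader might infer that an attendance requirement clashes with the home and ward provision. That provision is for rare cases and is tied to treatment disruption, so it can be read as continuity for people already enrolled. It calls for clarification and is not a proven conflict.

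**Conclusion.** The point holds in limited form. An operative eligibility rule is stated the wrong way round, nothing elsewhere in the protocol corrects it, and no waiver is available. It should be corrected because enrolling clinic attenders contravenes the criteria as they stand. The consequences are confined to eligibility checking, audit and clarity about who may be enrolled. No sample size, power or analysis figure is affected.

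The conclusion rests on the text of Sections 6.1, 6.2 and 13.5 as they appear in this version of the protocol. That the bullet is a slip is an inference, though a strong one, from the transport note and from the outpatient design.

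**What to change.** Amend the protocol in one of two ways: move the line from Section 6.2 to Section 6.1 as an inclusion criterion (able to attend the outpatient clinic, with free transport provided), or keep it in Section 6.2 and reword it as inability to attend.

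In the same amendment, add a sentence that reconciles the criterion with Section 7.1. It should state whether treatment at home or on a ward covers only disruption after enrolment, or also makes people who cannot attend eligible. That choice is the sponsor's; Sections 6.1, 6.2 and 7.1 need to agree on it.

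The cost is one corrected line and one clarifying sentence, submitted through the usual amendment route. The planned sample size and the analysis stay as they are.
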